3. INTRODUCTION

This SAP has been developed after review of the Clinical Study Protocol (final version dated 24 December 2016).

This SAP describes the planned analysis of the safety, tolerability, pharmacokinetic (PK) and pharmacodynamic (PD) data from this study. A detailed description of the planned TFLs to be presented in the clinical study report (CSR) is provided in the accompanying TFL shell document.

The intent of this document is to provide guidance for the statistical and PK analyses of data. In general, the analyses are based on information from the protocol, unless they have been modified by agreement between Eli Lilly and Company and Covance Early Clinical (EC) Biometrics. A limited amount of information concerning this study (e.g., objectives, study design) is given to help the reader's interpretation. This SAP must be signed off prior to first subject administration for this study. When the SAP and TFL shells are agreed upon and finalized, they will serve as the template for this study's CSR.

This SAP supersedes the statistical considerations identified in the protocol; where considerations are substantially different, they will be so identified. If additional analyses are required to supplement the planned analyses described in this SAP, they may be performed and will be identified in the CSR. Any substantial deviations from this SAP will be agreed upon between Eli Lilly and Company and Covance EC Biometrics and identified in the CSR. Any minor deviations from the TFLs may not be documented in the CSR.

This SAP is written with consideration of the recommendations outlined in the International Conference on Harmonisation (ICH) E9 Guideline entitled Guidance for Industry: Statistical Principles for Clinical Trials¹ and the ICH E3 Guideline entitled Guidance for Industry: Structure and Content of Clinical Study Reports².

4. STUDY OBJECTIVES

4.1 Primary Objective

- To explore the safety and tolerability of LY3337641 in healthy Japanese and Caucasian subjects.

4.2 Secondary Objective

- To estimate the PK parameters of single and multiple doses of LY3337641 following oral administration in healthy Japanese and Caucasian subjects.

[figure not shown]
4.3 Exploratory Objectives

- To explore the PD following single and multiple doses of LY3337641 in healthy Japanese and Caucasian subjects.

- To explore the safety, tolerability, PK, and PD of LY3337641 in Japanese subjects in relation to Caucasian subjects.
- To explore the effect of LY3337641 on ECG findings in healthy Japanese and Caucasian subjects.

5. STUDY DESIGN

This is a single-site, subject- and investigator-blind, randomized, placebo-controlled, single dose (SD) and multiple dose (MD) study to assess the safety, tolerability, PK, and PD of LY3337641 in healthy Japanese and Caucasian subjects. Subjects will be randomized to LY3337641 within each cohort as shown in Figure JPDB.1. All cohorts will be randomized in a 3:1 ratio of LY3337641 to placebo. MD Cohort 1 (30 mg once daily [QD] for 2 weeks) and Cohort 5 (optional) will consist of 12 subjects (8 Japanese and 4 Caucasian). SD Cohorts 2, 3, and 4 (5, 80, and 160 mg SD) will consist of 8 subjects (4 Japanese and 4 Caucasian). For each MD cohort, 6 Japanese subjects and 3 Caucasian subjects will receive LY3337641, while 2 Japanese subjects and 1 Caucasian subject will receive placebo. For each SD cohort, 3 Japanese subjects and 3 Caucasian subjects will receive LY3337641, while 1 Japanese subject and 1 Caucasian subject will receive placebo. Investigational product (IP) will be administered orally. Cohorts 1, 2, and 3 may be conducted in parallel if the site is able to accommodate more than 1 cohort at a time; however, priority will be given to dose Cohort 1, since the timing of this cohort will determine the timing of the interim analysis. Cohort 4 will be started based on the safety assessment up to Day 3 (48 hours postdose) of Cohort 2. If the dose level/regimen for Cohort 1 is not tolerated or there is a need to dose more subjects to assess safety, a daily dose of 30 mg or less (QD or twice daily [BID]) may be given in Cohort 5 based on the findings from Cohort 1. This will be discussed and agreed upon by the investigator and the Lilly clinical pharmacologist. The randomization rules and procedures will be the same as Cohort 1.

Abbreviations: BID = twice daily; FU = follow-up; JP = Japanese; LY = LY3337641; Pb = placebo; QD = once daily.

*Dose, regimen, and subject number may change for optional cohort.

Figure JPDB.1. Study Design

6. TREATMENTS

The following is a list of the study treatment abbreviations that will be used in the Safety TFLs.

Study Treatment Name	Treatment order in TFL
Pooled Placebo SD	1
LY3337641 5 mg SD	2
LY3337641 80 mg SD	3
LY3337641 160 mg SD	4
Pooled Placebo QD	5
LY3337641 30 mg QD (Day 1)*	6
LY3337641 30 mg QD (Day 15)*	7
LY3337641 TBD mg BID or QD	TBD

* Split by Day for vital signs and ECG data only.

The following is a list of the study treatment abbreviations that will be used in the PK TFLs.

Study Treatment Name	Treatment order in TFL
LY3337641 5 mg SD	1
LY3337641 30 mg QD (Day 1)	2
LY3337641 80 mg SD	3
LY3337641 160 mg SD	4
LY3337641 30 mg QD (Day 15)	5
LY3337641 TBD mg BID or QD	TBD

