| 12-Lead ECGg | X | | | -1, -0.5, 0, 0.5, 1, 2, 3, 4, 6, 12 | 24 ⁱ | 0 | 0 | 0 | 0, 0.5, 1, 2, 3, 4, 6, 12 | 24 | 48 | | | | X |
| Chest x-ray (posterior, anterior, and lateral) | X | | | | | | | | | | | | | | |
| Clinical laboratory measures (serum chemistry, hematology, urinalysis) | X | | | 0 | 24 ⁱ | | 0 | | | | 48 | | | | X |
| HBcAb, HBsAg, HCV, and HIV tests | X | | | | | | | | | | | | | | |
| Serum pregnancy test ^h | X | | | | | | | | | | | | | | |
| Urine pregnancy test ^h | | | X | | | | 0 | | 0 | | | | | | X |

| Visit | Screening | Treatment Period ^a | | | | | | | | Follow-Up ^a | | | | | |
|------------------------------|-----------|-------------------------------|----|----------------------------------------|-----------------|---|---|----|----------------------------------------|------------------------|----|----|----|----|------------|
| Study Day | ≤28 days | -2 | -1 | 1 ^b | 2 | 4 | 8 | 11 | 15 | 16 | 17 | 19 | 22 | 25 | 29/ EoS |
| FSH ^h | X | | | | | | | | | | | | | | |
| Drug and alcohol screen | X | X | | | | | | | | | | | | | |
| QuantiFERON®-TB Gold Plus | X | | | | | | | | | | | | | | |
| PK sampling: blood | | | | 0, 0.25, 0.5, 1, 2, 3, 4, 6, 8, 10, 12 | 24 ⁱ | 0 | 0 | 0 | 0, 0.25, 0.5, 1, 2, 3, 4, 6, 8, 10, 12 | 24, 36 | 48 | X | X | X | X |
| BTK occupancy | | | | 0, 1, 2, 4, 12 | 24 ⁱ | | 0 | | 0, 1, 2, 4, 12 | 24 | 48 | X | X | X | X |
| Skin inspection ^d | | | X | 0, 12 | 24 ⁱ | 0 | 0 | 0 | 0 | X | X | X | X | X | X |
| Non-PGx stored sample | | | | 0 | | | 0 | | | 24 | | | | | |
| PGx | | | | 0 | | | | | | | | | | | |

Abbreviations: AEs = adverse events; BTK = Bruton's tyrosine kinase; CRU = clinical research unit; ECG = electrocardiogram; EoS = end of study;

FSH = follicle-stimulating hormone; HBcAb = hepatitis B core antibody; HBsAg = hepatitis B surface antigen; HCV = hepatitis C virus; HIV = human immunodeficiency virus; IP= investigational product; PGx = pharmacogenomics; PK = pharmacokinetic; TB = tuberculosis.

Note: numbers are in hours in relation to dosing; 0 = predose.

- a All planned procedures will be done predose unless the time is indicated.
- b For twice-daily regimen, the time is based on the first dose. The second dose should be administered after sample collection for the 12-hour time point.
- c Subjects will be dosed every day from Day 1 through Day 15. For twice-daily regimen, only the morning dose will be administered on Day 15.

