9. STATISTICAL METHODOLOGY

9.1 General

Data listings will be provided for all data that is databased. Summary statistics and statistical analysis will only be presented for data where detailed in this SAP. For continuous data, summary statistics will include the arithmetic mean, arithmetic standard deviation, median, min, max and N; for log-normal data (e.g. the PK parameters: area under the concentration versus time curve [AUC] and maximum observed drug concentration [C_{max}]) the geometric mean and geometric coefficient of variation (CV%) will also be presented. For categorical data, frequency count and percentages will be presented. Data listings will be provided for all subjects up to the point of withdrawal, with any subjects excluded from the relevant population highlighted. Summary statistics and statistical analyses will generally only be performed for subjects included in the relevant analysis population. For the calculation of summary statistics and statistical analysis, unrounded data will be used.

Mean change from baseline is the mean of all individual subjects' change from baseline values. Each individual change from baseline will be calculated by subtracting the individual subject's baseline value from the value at the timepoint. The individual subject's change from baseline values will be used to calculate the mean change from baseline using a SAS procedure such as Proc Univariate.

Data will be also summarized by population (overall, Japanese and Caucasian) where appropriate.

Data analysis will be performed using SAS[®] Version 9.3 or greater.

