9.6.5 Electrocardiogram (ECG)

The ECG data will be obtained directly from the 12-lead ECG traces. These data include the PR, QT, QRS duration and heart rate. In addition, QTcF (the QT interval corrected using Fridericia's formula) will be calculated as follows:

$$QTcF = \frac{QT}{\sqrt[3]{(60/HR)}}$$

The ECGs will be collected in triplicate; the mean of triplicates will be used in the analysis. The ECG data will be summarized by population and treatment together with changes from baseline, where baseline is defined as the mean of the Day 1 predose measurements. Figures of mean ECG data and mean changes from baseline will be presented by population and treatment. As

suggested by ICH E14 Guideline, the frequency of subjects with a maximum increase from baseline in QTcF interval will be summarized for each population and treatment according to the following categories: >30 ms and >60 ms. In addition, the frequency of subjects with QTcF postdose values, according to the following categories: >450 ms, >480 ms and >500 ms, will be summarized by population and treatment.

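### SAP 6 splits LY 30 mg QD by day for ECG but not Pooled Placebo QD, so the categorical QTcF counts would judge placebo over about twice as many ECG times

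*SAP*

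**What the plan says.** SAP section 6 introduces its first table with "The following is a list of the study treatment abbreviations that will be used in the Safety TFLs". In the multiple-dose block that table has "Pooled Placebo QD" as one unmarked row, followed by LY3337641 30 mg QD (Day 1) and LY3337641 30 mg QD (Day 15). Only the two LY rows carry the asterisk, which is explained as "Split by Day for vital signs and ECG data only".

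SAP 9.6.5 then states that "the frequency of subjects with a maximum increase from baseline in QTcF interval will be summarized for each population and treatment", with cut-offs of >30 and >60 ms. It adds a second count, again by population and treatment, of subjects with postdose QTcF above 450, 480 and 500 ms. Neither count has a day or visit window. Change is measured from one fixed point: "baseline is defined as the mean of the Day 1 predose measurements".

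In the protocol's Schedule of Activities for Cohorts 1 and 5, the ECG row gives seven postdose times on Day 1 and one on Day 2. For Days 4, 8, 11, 15, 16 and 17 it reads "0 | 0 | 0 | 0, 0.5, 1, 2, 3, 4, 6, 12 | 24 | 48". A last ECG falls on Day 29.

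Two statements limit what can be concluded. SAP 9.1 says "Summary statistics and statistical analysis will only be presented for data where detailed in this SAP", so visits outside the two profiles may be meant for listings only. SAP section 3 says that the detailed description of the outputs "is provided in the accompanying TFL shell document", and that document was not supplied.

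**The concern.** A subject's maximum over a set of readings cannot fall when readings are added. The same holds for whether any postdose value crosses a threshold. If the categorical QTcF tables are built on the rows as listed, a whole-course placebo row stands beside two part-course LY rows. The percentages in that block are then not like for like. With no drug effect the mismatch tends to make placebo look worse relative to LY, which is the unhelpful direction in a safety table.

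The problem is confined to the multiple-dose block. In the single-dose block neither placebo nor LY is split, and Cohorts 2 to 4 share one ECG schedule. Within the multiple-dose block it affects only counts pooled over time. Summaries shown time by time, the listings and the concentration-QTcF model in SAP 9.6.7 do not depend on it.

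**Working it through.** **1. Count the ECG times.** The documents state no count, so there is no figure to reproduce. From the Cohort 1 and 5 schedule, the times after the first dose are: Day 1, 7 (0.5 to 12 h); Day 2, 1; Days 4, 8 and 11, 3; Day 15, 8 (predose plus 7); Days 16 and 17, 2; Day 29, 1. The total is 7 + 1 + 3 + 8 + 2 + 1 = 22. The SAP does not say which visits the Day 1 and Day 15 rows cover, so several windows are shown.

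| Window | Placebo (unsplit) | LY Day 1 row | LY Day 15 row |
|---|---|---|---|
| Every visit allocated | 22 | 7 + 1 + 3 = 11 | 8 + 2 + 1 = 11 |
| Two profiles with 24 h and 48 h readings | 18 | 7 + 1 = 8 | 8 + 2 = 10 |
| Days 1 and 15 only, with Day 15 predose | 15 | 7 | 8 |
| Days 1 and 15, postdose only | 14 | 7 | 7 |

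**2. Direction.** In each line the placebo window contains each LY window. With no drug effect, the chance of exceeding any threshold is therefore at least as high in the placebo row. This needs no assumption about variability.

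**3. Size for >30 ms.** The documents give no QTcF variability, so these inputs are assumptions: within-day SD 8 ms and day-to-day SD 6 ms as the base case, with a grid of 6, 8, 10 ms by 4, 6, 8 ms. There is no drug effect. The model is

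change at time t on day d = (D_d − D_1) + e_t − (mean of three Day 1 predose errors),

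with independent normal day effects D and within-day errors e. In the base case a later-day change has SD √(2×36 + 64 + 64/3) = 12.5 ms. A Day 1 change has SD √(64 + 64/3) = 9.2 ms, because the day effect cancels. Day 1 readings therefore add fewer exceedances, which is why doubling the readings does not double the percentage. Results by Monte Carlo, 4,000,000 subjects per scenario (ratios from unrounded percentages):

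| Placebo times vs LY Day 15 times | Base case, chance of >30 ms | Ratio, base case | Ratio over the grid |
|---|---|---|---|
| 22 vs 11 | 8.5% vs about 6.2% | about 1.4 | 1.35–1.54 |
| 18 vs 10 | 6.5% vs 5.6% | 1.16 | 1.12–1.38 |
| 15 vs 8 | 4.7% vs 4.4% | 1.08 | 1.00–1.39 |
| 14 vs 7 | 4.3% vs 4.0% | 1.09 | 1.00–1.44 |

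A mixed pairing of 22 placebo times with 8 LY times (placebo over all visits, LY over Day 15 alone) gives 8.5% vs 4.4%, with a grid range of 1.89–2.19. Absolute levels are not known: over the grid, the placebo chance over 22 times runs from about 0.5% to 25%. The gap to the LY Day 1 row has the same direction (LY 0.4–3.4% in the base case), but no ratio is given because it depends mainly on the assumed day-to-day SD.

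**4. Other cut-offs.** The chance of >60 ms is at most 0.14% in any row and scenario. The >450, >480 and >500 ms counts have the same structural mismatch. Its size was not computed because no baseline QTcF is given.

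**5. What the table would show.** Take one multiple-dose cohort, with 3 placebo and 9 LY subjects, and the LY Day 15 row at 10 times (5.6%). The chance that no placebo subject exceeds 30 ms is (1 − 0.085)³ = 77% over 22 times, (1 − 0.065)³ = 82% over 18 times and (1 − 0.056)³ = 84% with matched windows. Comparing Bin(3, p) with Bin(9, 0.056) exactly gives:

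| Placebo window | Placebo % higher | LY % higher | Tie |
|---|---|---|---|
| 22 times (mixed pairing) | 23% | 31% | 46% |
| 18 times | 18% | 33% | 49% |
| 10 times (matched) | 16% | 34% | 50% |

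**The case against.** The strongest reply is that SAP section 6 gives only labels and a display order. It defines no window or denominator. The same Day 1 and Day 15 labels appear in the PK list, where they are needed, and they are natural for mean profiles. The shells may show one overall LY row for the categorical counts, and the mismatch would then disappear. This stands in part: an error in the output is not shown. But section 6 says that its rows are used in the safety outputs, 9.6.5 counts by treatment, and nothing in either document splits placebo or assigns Days 4, 8, 11 and 29. A programmer who follows the SAP as written would produce unequal windows.

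The second reply is that the effect is negligible with 3 placebo subjects: the placebo percentage for one cohort can only be 0, 33, 67 or 100. This stands as a limit on weight. Moving from matched windows to 18 against 10 shifts the three outcomes by only one or two percentage points.

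A reader might infer that twice the readings means twice the exceedances, or that the table is set up to mask a QT effect. The documents support neither. A ratio near 2 needs the mixed pairing of 22 against 8, which no passage prescribes. An LY exceedance inside either row is still displayed.

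**Conclusion.** The point holds as a minor inconsistency. SAP 6 read with 9.6.5 gives placebo about twice the ECG times of either LY 30 mg QD row in both sets of categorical QTcF counts. With no drug effect the placebo percentage tends to be inflated relative to LY. For >30 ms against the LY Day 15 row, the factor is about 1.35 to 1.54 with every visit allocated and 1.0 to 1.4 on profile windows. It reaches about 2 only if the Day 15 row is limited to Day 15 while placebo uses all visits.

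The counts come from the schedule and the direction needs no variability assumption; the ratios rest wholly on assumed SDs. The tables are descriptive, the ECG objective is exploratory, and the small placebo group matters more than the window. The conclusion is conditional on the shells using the rows as listed.

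**What to change.** For the categorical QTcF summaries, use one overall LY3337641 30 mg QD row and one overall Pooled Placebo QD row over all postdose ECG times (22 in each arm). Alternatively, apply identical Day 1 and Day 15 windows to both arms. In either case, state which row takes Days 4, 8, 11 and 29, so that no LY exceedance at those visits is left out. If the shells already do this, say so in SAP 6 or 9.6.5.

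The cost is one footnote to the treatment list or one sentence in 9.6.5, plus a check of the table shell. No new data are needed.

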7. SAMPLE SIZE JUSTIFICATION

Up to 60 subjects may be enrolled so that approximately 36 to 48 subjects complete the study. The sample size is customary for Phase 1 studies evaluating safety, PK, and/or PD parameters and is not based on the power of statistical hypothesis tests. Subjects who are randomized but discontinue the study may be replaced in the same cohort and race (Japanese or Caucasian) at the discretion of the sponsor.

8. DEFINITION OF ANALYSIS POPULATIONS

The “Safety” population will consist of all subjects who received at least one dose of LY3337641 or placebo, and have at least one postdose safety assessment.

The “Pharmacokinetic” population will consist of all subjects who received at least one dose of LY3337641 and have evaluable PK data.

The “Pharmacodynamic” population will consist of all subjects who received at least one dose of LY3337641 or placebo and have evaluable PD data

All protocol deviations that occur during the study will be considered for their severity/impact and will be taken into consideration when subjects are assigned to analysis populations.

9. STATISTICAL METHODOLOGY

9.1 General

Data listings will be provided for all data that is databased. Summary statistics and statistical analysis will only be presented for data where detailed in this SAP. For continuous data, summary statistics will include the arithmetic mean, arithmetic standard deviation, median, min, max and N; for log-normal data (e.g. the PK parameters: area under the concentration versus time curve [AUC] and maximum observed drug concentration [C_{max}]) the geometric mean and geometric coefficient of variation (CV%) will also be presented. For categorical data, frequency count and percentages will be presented. Data listings will be provided for all subjects up to the point of withdrawal, with any subjects excluded from the relevant population highlighted. Summary statistics and statistical analyses will generally only be performed for subjects included in the relevant analysis population. For the calculation of summary statistics and statistical analysis, unrounded data will be used.

Mean change from baseline is the mean of all individual subjects' change from baseline values. Each individual change from baseline will be calculated by subtracting the individual subject's baseline value from the value at the timepoint. The individual subject's change from baseline values will be used to calculate the mean change from baseline using a SAS procedure such as Proc Univariate.

Data will be also summarized by population (overall, Japanese and Caucasian) where appropriate.

Data analysis will be performed using SAS[®] Version 9.3 or greater.

9.2 Demographics and Subject Disposition

Subject disposition will be listed. The demographic variables age, sex, race/subcategory, ethnicity, country of enrolment, site ID, body weight, height and body mass index will be summarized by population and listed. All other demographic data, including associated person demographics, will be listed only.

9.3 Pharmacokinetic Assessment

9.3.1 Pharmacokinetic Analysis

PK parameter estimates for LY3337641 will be calculated by standard noncompartmental methods of analysis. The PK analysis of this study will be the responsibility of Eli Lilly and Company.

9.3.2 Pharmacokinetic Statistical Methodology

Dose proportionality among the 5 mg, 30 mg (Day 1), 80 mg and 160 mg dose levels will be assessed using a power model.

The PK parameters C_{max} , $AUC_{0-\infty}$, and AUC_{0-24} will be assessed separately using a power model as follows:

$$\log(PK_i) = \alpha + \beta_i \cdot \log(dose_i) + \varepsilon_i$$

where i represents the i th subject, PK represents a pharmacokinetic parameter (AUC or C_{max}), and ε_i is a residual error term. The dose proportionality will be reported as the estimated ratio of dose-normalized means

$$\hat{R}_{dnm} = \left(\frac{h}{l}\right)^{\hat{\beta}_1 - 1}$$

and its 90% CI, where h and l denote the highest and lowest doses included in the model, respectively. The estimates of β along with its 90% CI, predicted geometric mean, and ratio of dose normalized geometric mean will be reported for each parameter.

The following SAS code will be used:

```
proc mixed data=pk;
  by parameter;
  model lpk = ldose / alpha=0.1 residual ddfm=kr;
  estimate 'xx mg' intercept 1 ldose yy / cl;
  estimate 'zz mg - xx mg' ldose pp / alpha=0.1 cl;
  ods output solutionf=est;
  ods output estimates=estims;
run;
```

The above analysis will be repeated for Japanese and Caucasian subjects separately to examine the effect of the population on dose proportionality.

The PK summary tables and figures will be the responsibility of Eli Lilly and Company.

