- d Assessment should be performed every day during the subject's stay at the CRU.
- e Height will be measured at screening only. Body weight will be measured in the morning.
- f Refer to Section 9.4.2 for instructions on vital signs.
- g Refer to Section 9.4.3 for instructions on ECGs. ECGs should be administered after subject has been resting in the supine position for approximately 5 minutes. On days without dosing, ECGs should be administered close to the Day 1 dosing time, when possible. ECGs will be collected in triplicate except at the screening visit.
- h All female subjects of childbearing potential will undergo a serum pregnancy test at screening. For women who are considered postmenopausal, FSH should be drawn to confirm postmenopausal status as defined in inclusion criterion [1b] and exemption from further pregnancy tests (urine) during the study.
- i This 24-hour sample is to be taken predose.

Study Schedule Protocol I8K-JE-JPDB (Cohorts 2, 3, and 4)

| Visit | Screening | Treatment Period ^a | | | Follow-Up ^a | | | | | |
|-------------------------------------------------------------------------|-----------|-------------------------------|----|-------------------------------------|------------------------|----|---|---|----|--------|
| Study Day | ≤28 days | -2 | -1 | 1 | 2 | 3 | 5 | 8 | 11 | 15/EoS |
| Inpatient stay at CRU | | ←—————→ | | | | | | | | |
| Informed consent | X | | | | | | | | | |
| Review eligibility | X | | X | | | | | | | |
| Randomization | | | | X | | | | | | |
| IP administration | | | | X | | | | | | |
| Complete medical history | X | | | | | | | | | |
| Review preexisting conditions/AEs | X | X | X | X | X | X | X | X | X | X |
| Review concomitant medications | X | X | X | X | X | X | X | X | X | X |
| Complete physical examination | X | | | | | X | | | | X |
| Symptom-directed physical examination | | X | X | X | X | | X | X | X | |
| Body weight and height ^b | X | | X | | | X | | | | X |
| Vital signs (pulse rate, blood pressure, body temperature) ^c | X | | 0 | 0, 1, 2, 4, 12 | 24 | 48 | | | | X |
| 12-Lead ECG ^d | X | | | -1, -0.5, 0, 0.5, 1, 2, 3, 4, 6, 12 | 24 | 48 | | | | X |
| Chest x-ray (posterior, anterior, and lateral) | X | | | | | | | | | |
| Clinical laboratory measures (serum chemistry, hematology, urinalysis) | X | | | 0 | | 48 | | | | X |
| HBcAb, HBsAg, HCV, and HIV tests | X | | | | | | | | | |
| Serum pregnancy test ^e | X | | | | | | | | | |
| Urine pregnancy test ^e | | | X | | | | | | | X |

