| FSH ^e | X | | | | | | | | | |

| Visit | Screening | Treatment Period ^a | | | Follow-Up ^a | | | | | |
|---------------------------|-----------|-------------------------------|----|----------------------------------------|------------------------|----|---|---|----|--------|
| Study Day | ≤28 days | -2 | -1 | 1 | 2 | 3 | 5 | 8 | 11 | 15/EoS |
| Drug and alcohol screen | X | X | | | | | | | | |
| QuantiFERON®-TB Gold Plus | X | | | | | | | | | |
| PK sampling: blood | | | | 0, 0.25, 0.5, 1, 2, 3, 4, 6, 8, 10, 12 | 24, 36 | 48 | | X | | X |
| BTK occupancy | | | | 0, 1, 2, 4, 12 | 24 | 48 | | X | | X |
| Skin inspection | | | X | 0, 12 | X | X | X | X | X | X |
| Non-PGx stored sample | | | | 0 | | | | X | | X |
| PGx | | | | 0 | | | | | | |

Abbreviations: AEs = adverse events; BTK = Bruton's tyrosine kinase; CRU = clinical research unit; ECG = electrocardiogram; EoS = end of study;

FSH = follicle-stimulating hormone; HBcAb = hepatitis B core antibody; HBsAg = hepatitis B surface antigen; HCV = hepatitis C virus; HIV = human immunodeficiency virus; IP= investigational product; PGx = pharmacogenomics; PK = pharmacokinetic; TB = tuberculosis.

Note: numbers are in hours in relation to dosing; 0 = predose.

- a All planned procedures will be done predose unless the time is indicated.
- b Height will be measured at screening only. Body weight will be measured in the morning.
- c Refer to Section 9.4.2 for instructions on vital signs.
- d Refer to Section 9.4.3 for instructions on ECGs. ECGs should be administered after subject has been resting in the supine position for approximately 5 minutes. On days without dosing, ECGs should be administered close to the Day 1 dosing time, when possible. ECGs will be collected in triplicate except at the screening visit.
- e All female subjects of childbearing potential will undergo a serum pregnancy test at screening. For women who are considered postmenopausal, FSH should be drawn to confirm postmenopausal status as defined in inclusion criterion [1b] and exemption from further pregnancy tests (urine) during the study.

3. Introduction

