10.3.2. Pharmacokinetic Analyses

10.3.2.1. Pharmacokinetic Parameter Estimation

PK parameter estimates for LY3337641 will be calculated by standard noncompartmental methods of analysis.

In the SD cohorts, the primary parameters for analysis will be C_{\max} , area under the concentration versus time curve from zero to infinity ($AUC_{0-\infty}$), and area under the concentration versus time curve from 0 to 24 hours (AUC_{0-24}) of LY3337641. In the MD cohorts, the primary parameters to be calculated will include C_{\max} (or C_{\max} during a dosing interval at steady state [$C_{\max,ss}$]) and area under the concentration versus time curve during the dosing interval ($AUC_{0-\tau}$) of LY3337641 after the first and last dose of IP. Other noncompartmental parameters, such as half-life, apparent clearance, apparent volume of distribution, and accumulation ratio (MD period only), may be reported.

Additional analysis may be conducted if appropriate.

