10.3.2.2. Pharmacokinetic Statistical Inference

The dose proportionality of selected LY3337641 PK parameters, including log transformed C_{\max} and relevant AUC values will be examined for all subjects and for each population across the entire dose range using a power model approach (Smith et al. 2000) to estimate the slope of the power model, which represents the ratio of dose-normalized geometric means. Exploratory power model analysis based on the model including race and race-by-dose interaction terms will also be performed to examine the effect of the race on dose proportionality.

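### Does pooling 30 mg Day 1 profiles that end at 24 h with single-dose profiles sampled to Day 15 undermine the AUC0-inf power model?

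*SAP*

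**What the plan says.** SAP 9.3.2 sets one power model for Cmax, AUC0-inf and AUC0-24: "Dose proportionality among the 5 mg, 30 mg (Day 1), 80 mg and 160 mg dose levels will be assessed using a power model". It reports the slope, the ratio of dose-normalized means (R_dnm) with its 90% CI, and the "predicted geometric mean, and ratio of dose normalized geometric mean will be reported for each parameter". The only planned repeat fits are by race.

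The 30 mg level comes from Cohort 1, which is dosed daily. In the protocol's Schedule of Activities for Cohorts 1 and 5, the first-dose profile runs from predose to 12 h and then has a 24-h sample. Footnote i to that table says of it: "This 24-hour sample is to be taken predose". The schedule for Cohorts 2, 3 and 4 samples to 12 h, then at 24, 36 and 48 h, on Day 8 and on Day 15.

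Protocol 10.3.2.1 names AUC0-inf as a primary parameter for the single-dose cohorts. For the others it says "In the MD cohorts, the primary parameters to be calculated will include" Cmax and AUC over the dosing interval, after both the first and the last dose. It adds: "Other noncompartmental parameters, such as half-life, apparent clearance, apparent volume of distribution, and accumulation ratio (MD period only), may be reported". Protocol 10.3.2.2 asks for dose proportionality "for all subjects and for each population across the entire dose range using a power model approach".

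**The concern.** For AUC0-inf the length of the sampling window is tied to dose level: 24 h at 30 mg and up to 336 h at 5, 80 and 160 mg. If the drug has a slow terminal phase, a profile that ends at 24 h fits too steep a terminal slope and extrapolates too little. The 30 mg AUC0-inf would then be low for a reason unrelated to dose. An ordinary cap on the extrapolated share would not catch this, because the missed phase also makes that share look small. The 30 mg group is 6 of 15 active Japanese subjects (40%) but 3 of 12 Caucasian subjects (25%), so the distortion could also differ between the two refits. Half-life by dose level would reveal it, but reporting half-life is optional. At stake are the dose-proportionality result and the predicted AUC0-inf means.

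**Working it through.** **Inputs.** Active subjects per protocol 5.1: Cohort 1 has 6 Japanese + 3 Caucasian = 9, and each single-dose cohort has 3 + 3 = 6. The model therefore has 9 + 3 × 6 = 27 subjects, split 6/9/6/6 over 5/30/80/160 mg (optional Cohort 5 excluded). The documents give no CV or half-life, so those below are assumptions.

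**The plan's own figures.** Appendix 5 of the protocol gives at most 33 and 16 PK samples. From the schedules: 11 + 1 + 3 + 11 + 2 + 1 + 4 = 33 for the multiple-dose cohorts and 11 + 2 + 1 + 2 = 16 for the single-dose cohorts. Both agree, so the windows are read correctly. The 36 to 48 completers also agree: 12 + 3 × 8 = 36, and 48 with Cohort 5.

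**Effect of a low 30 mg value on the fit.** Let x = log dose. Mean x = 3.593 and Sxx = 40.855. If 30 mg reads a fraction s low, the log bias is δ = ln(1 − s).

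- Slope shift = δ × 9 × (ln 30 − 3.593)/40.855 = −0.0422 × δ. At s = 20%, δ = −0.223 and the shift is +0.009.
- R_dnm is multiplied by 32^shift, where 32 = 160/5.
- Predicted log mean at x shifts by δ × 9/27 + slope shift × (x − 3.593). At s = 20% and 5 mg: −0.0744 + 0.0094 × (1.609 − 3.593) = −0.093, or 8.9% low. At 160 mg it is 5.9% low.
- 90% half-width of the slope at an assumed 40% CV (σ = √ln 1.16 = 0.385): t(0.95, 25) × 0.385/√40.855 = 0.103. The R_dnm CI factor is 32^0.103 = 1.43.

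| 30 mg low by | slope shift | R_dnm factor | predicted means low by |
|---|---|---|---|
| 10% | +0.005 (rounded up from 0.0045) | 1.016 | 3-4% |
| 20% | +0.009 | 1.033 | 6-9% |
| 25% | +0.012 | 1.043 | 8-11% |

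The slope barely moves because 30 mg lies close to the geometric mean dose, exp(3.593) = 36.3 mg. The predicted means have 90% CI factors of 1.14-1.27. In the refits at 20% low, they are 7.0-10.5% low in Japanese and 4.4-6.8% low in Caucasian subjects.

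**How low could 30 mg read?** With single-phase elimination (assumed half-life 3-24 h), both windows recover at least 99% of AUC0-inf, so there is no bias. For a slow phase, 18 two-phase profiles were assumed: absorption rate 1.5/h; fast half-life 3 or 4 h; slow half-life 12, 24 or 48 h; slow share of AUC 10, 30 or 50%. AUC was linear-up/log-down with the terminal slope from the last three points. Relative to the single-dose schedule, 30 mg reads 2-29% low (median 7%) with no assay limit, and 0-25% low (median 4%) with a limit of 1% of Cmax. It is under 10% low in 10 and 12 of the 18 profiles respectively. The extrapolated share at 30 mg is 1-13%.

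**What the plan already offers.** Under linear, time-invariant kinetics, steady-state AUC over the dosing interval equals first-dose AUC0-inf. On the same grid, Day 15 AUC0-tau recovers at least 99.7% of the true value. Day 1 AUC0-inf falls short of it by about 2-28% (median about 6%), so it shows nearly the same mismatch within the same nine subjects. Cohort 1 is also sampled after its last dose to Day 29.

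**What a single-dose-only fit would add.** Its slope half-width is 0.106 against 0.103, so it costs little precision. But a real assay limit is a fixed concentration and cuts the 5 mg profile first. With a limit at 1% of the 30 mg Cmax (assumed), 5 mg reads up to 29% low on the same grid. The median slope bias is then 0.020 in the single-dose-only fit and 0.022 in the four-level fit. A 20% shortfall at 5 mg moves the single-dose-only slope by 0.069, about seven times the effect of the same shortfall at 30 mg (0.069/0.0094 = 7.3). A rule to quote single-dose-only means when the two fits differ by more than 10% at any dose would, by simulation at 40% CV, fire in 13% of data sets with no bias and in 43% when 30 mg is 20% low. It would miss that bias 57% of the time.

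**The case for a change.** The best case for a change is that the gap is certain and cheap to close: a few sentences and one extra model run, with no subject leaving the main fit. The SAP must be signed off before first dosing, so a rule could be fixed before any data are seen, whereas choosing later which AUC0-inf means to quote would be data-driven. AUC0-24 is not a full answer, since a predicted mean is promised for AUC0-inf as well. Comparing Japanese with Caucasian PK is an exploratory objective, and the two refits are unequally exposed.

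Much of this stands. The windows do differ, a 20% cap on extrapolation would not flag the problem, and the first- versus last-dose comparison is not itself pre-specified, though both inputs will exist. That comparison also relies on time-invariant kinetics. The unequal exposure is real but small: at 20% low, the refits differ by about 2.5 to 4 percentage points in predicted means.

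What does not stand is that the extra fit would settle the matter. It aligns scheduled windows rather than usable ones, it predicts 30 mg with no 30 mg data across a 16-fold dose gap, and the switching rule is unreliable.

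**Conclusion.** No change to the plan is needed. The four-level fit follows protocol 10.3.2.2, and protocol 10.3.2.1 does not rule out AUC0-inf for the multiple-dose cohorts, so the two documents do not conflict. The dose-proportionality result is robust: even at 20% low, the slope and R_dnm move by a small fraction of their intervals. The remaining exposure is 6-9% in the model-predicted AUC0-inf means, for a secondary, estimation-only objective with no powered hypothesis. It arises only if there is a slow phase beyond 24 h. The readable text gives no half-life, and the dose justification is blacked out, so the sponsor may well know the answer. Observed geometric means for the single-dose levels (SAP 9.1) are free of the mismatch, as are the Cmax and AUC0-24 fits.

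A careful PK analyst would look at half-life, last quantifiable time and extrapolated share by dose level, and would set 30 mg Day 1 AUC0-inf against Day 15 AUC0-tau. The plan already permits this, since protocol 10.3 and SAP 3 both allow additional analyses. The figures rest on an assumed 40% CV, the assumed two-phase grid, full planned enrolment and no Cohort 5.
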